9.6 Data Management

9.6.1 Database

Data entered in the eCRF will be stored centrally in a database, which is maintained according to current standards for hard- and software (21CFR11 compliance, i.e. includes an audit trail) security, including daily backups and access to the data files only for investigators and/or qualified study staff involved in the DUS. The sponsor will only have access to pseudonymised data. For the HES-accredited DUS study sites, the CRO will assign a secure login for investigators and/or qualified study staff, who will be responsible for documentation. Access for respective staff members will be granted depending on their roles and tasks, and documented in the site delegation log. The secure login allows the investigators and/or qualified study staff to enter the data into the eCRF.

9.6.2 Patient Data Pseudonymisation

Patient data investigated (variables specified in [Section 9.3](#)) will be pseudonymised (a unique identifier) to secure the confidentiality of the patients' data. This will allow for any subsequent enquiries in relation to possible incomplete or inconclusive data to be resolved by the participating hospital.

Only pseudonymised data will be passed to the sponsor or published if applicable. The sponsor will not be able to backtrack to the identification of the patient.

The participating hospital staff will keep the coding/encryption key for the pseudonyms so that it is still possible for them to identify the individual patients, if required. Coding/encryption keys to identify patients will be kept separate from the rest of the data files, all of which will be maintained in password-protected servers and/or locked file cabinets. Hence, the codes/encryption keys will be accessible for investigators and/or qualified study staff only and if applicable for inspections by authorities. Keeping the codes during the conduct of the study will allow for clarification of data discrepancies.

For data protection reasons, onsite monitoring is not possible in this study, i.e. no personnel other than hospital staff will have access to patient records. Instead, data entry should be conducted by applying the four-eyes principle i.e. source data verification will be performed by two persons on indication and contraindications ([Section 9.8.1](#)). In case of unresolved discrepancies, the final decision will be taken by the local principal investigator at the respective study site.

After endorsement of the final study report by EMA/PRAC, the codes to identify patients will be destroyed by the investigator.

9.7 Data Analysis

9.7.1 Methods

Due to the exploratory character of this study only descriptive statistics will be used for the analysis of the variables listed in [Section 9.3](#). For continuous variables, mean \pm standard deviation, median and quartile (25th; 75th percentile) and numbers of non-missing and missing values will be presented. For categorical variables, frequencies and percentage will be shown for each category and for missing values.

Primary Variable

To assess the non-adherence of hospital physicians to the approved European PIs of HES 130 solutions (see Annex 1a/1b), the primary variable will be the number and proportion of patients whose treatment during the hospital stay did not adhere to the approved European PIs regarding indication, contraindications and dosage (posology)**. The full analysis set will comprise all eligible patients.

The number and percentage of patients who received HES 130 and were documented as non-adherent to one or more of the specifications made in the PIs (concerning the indication, contraindications and dosage) will be evaluated for the overall patient population and will be displayed together with 95 % confidence intervals for the percentage.

For the primary analysis, missing data regarding indication and posology (dosage) will neither be defined as non-adherent nor adherent prescription; this also applies if “not possible to conclude due to retrospective design” is assessed regarding indication. If more than one HES 130 prescription is reported for the same patient, every single prescription needs to adhere to the approved European PIs for counting the patient's total HES 130 treatment as adherent. That means, if at least one prescription will be non-adherent, the patient's total HES 130 treatment will be counted as non-adherent (see also Figure 3 and Figure 4 below).

Sensitivity Analyses of the Primary Variable

In addition, sensitivity analyses of the primary variable will be conducted in which “not possible to conclude due to retrospective design” regarding indication will be evaluated as

- non-adherent prescription (sensitivity analysis 1)
- adherent prescription (sensitivity analysis 2)

** Infusion of HES 130 for > 24 hours is considered as off-label use. Infusion of > 30 ml/kg for 24 hours of HES 130 (6 %) and > 18 ml/kg of HES 130 (10 %) for 24 hours is considered as off-label use.

Furthermore, sensitivity analyses regarding the contraindications of special interest (critically ill, sepsis, renal impairment)[#] will be done. For these, missing values will be evaluated as

- non-adherent prescription (sensitivity analysis 3)
- adherent prescription (sensitivity analysis 4)

Further Analyses

Similar to the analysis of the primary variable, non-adherence to individual specifications made in the PIs will be evaluated (i.e. HES 130 use outside indication, presence of any contraindication at the start time of HES 130 infusion, presence of contraindications at the start time of HES 130 infusion by each type of contraindication and dosage outside the specifications made in the PIs).

Additionally, the number and percentage of patients whose treatment during the hospital stay does not adhere to one or more specifications made in the approved European PIs [concerning the indication, contraindications and dosage (posology)] will also be evaluated for each country.

[figure not shown]
Furthermore, analysis of non-adherence to one or more specifications made in the approved European PIs (concerning the indication, contraindications and dosage [posology]) will also be conducted for each single HES 130 prescription as statistical unit for assessment (instead of considering the patient as statistical unit) and will be presented as secondary measure.

For this purpose, each prescription is defined as a treatment with a single or multiple HES 130 infusion(s) in a row until a change of the following occurred (see also Figure 1 above):

- Indication at start time of HES 130 infusion OR
- Trade name OR
- Prescribing physician OR
- Main medical procedure at start time of HES 130 infusion OR
- The subsequent HES 130 infusion was interrupted from the previous HES 130 infusion by a HES-free interval of ≥ 24 h (see example in Figure 3). To minimise calculation errors by the sites this definition will be applied technically (and is therefore not defined in [Section 9.3](#), Figure 1).

[figure not shown]
[#] Main focus of PRAC

Figure 3 Example A for Prescription

In case the treatment duration (including HES-free interval(s) of < 24 h) exceeded 24 h and comprised several single prescriptions as defined above, only prescriptions exceeding the 24 h period will be regarded as non-adherent (see example in Figure 4 prescriptions 3 and 4).

Figure 4 Example B for Prescription

Analyses of non-adherence according to (i) hospital type, and (ii) patients' age category will be conducted on patient level as primary statistical unit of the study as well as on prescription level. Additionally, analysis of non-adherence according to hospital wards will be performed on prescription level.

Furthermore, the medical procedures will be evaluated; details will be described in the statistical analysis plan.

Mean cumulative and mean maximum daily dose will be calculated for analysis of exposure to HES products for the overall patient population.

Missing/implausible data in the eCRF will be detected via automatic edit checks by the electronic data capture (EDC) system, during data entry. Implausible data can be detected automatically and/or manually and prompted to be corrected. Missing/implausible data will be followed up by the CRO data management with the investigator. Data that remain missing will not be imputed.

Further details of the analysis will be described in a statistical analysis plan which will be finalised prior to database closure.

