9.5 Study Size

The sample size calculation is based on the primary statistical unit of the study: Patients treated with HES 130.

For potential non-adherence rates of 5 % to 95 % and aiming for a precision (defined as the confidence interval width) of up to 5 percent points of the exact two-sided 95 % confidence interval (according to Clopper-Pearson) for the evaluation of non-adherence, a sample size of 1574 patients is required. To compensate for potential cases where the indication for use has been assessed as “not possible to conclude due to retrospective design” or missing data regarding posology (assumption of 10 %), 1749 patients will be documented.

In case the intended targeted sample size of 1749 could not be reached in the documentation period, analysis with a sample size of 1220 (including 10 % compensation for cases assessed as “not possible to conclude due to retrospective design” or missing data regarding posology) will be performed to ensure a precision (confidence interval width) of at least 6 percent points.

However, the sponsor will make any effort to reach the intended target sample size of 1749.

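### Sensitivity analyses 1 to 4 never test missing posology or a blank indication and never move the unknowns together, so their span can be narrower than the data allow

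*Protocol*

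**What the plan says.** **Primary rule (Protocol 9.7.1, Primary Variable).** The protocol states that "missing data regarding indication and posology (dosage) will neither be defined as non-adherent nor adherent prescription", and applies the same treatment to an indication that the investigator could not conclude on. Three states are thus set aside: blank indication, missing posology, inconclusive indication. The full analysis set is all eligible patients, and one non-adherent prescription makes the patient non-adherent.

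**Sensitivity analyses (Protocol 9.7.1).** The first pair is introduced with "sensitivity analyses of the primary variable will be conducted in which" the inconclusive indication counts as non-adherent (analysis 1) or adherent (analysis 2). The second pair concerns critical illness, sepsis and renal impairment: "For these, missing values will be evaluated as" non-adherent (analysis 3) or adherent (analysis 4). The same section later says that data which remain missing will not be imputed.

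**What the plan expects to be unknown (Protocol 9.5).** The sample size allows for inconclusive indications or "missing data regarding posology (assumption of 10 %), 1749 patients will be documented".

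**How an unknown indication is recorded (Protocol 9.3).** The eCRF question offers yes, no or an inconclusive answer, so a blank is a fourth state. The primary rule also lists it separately.

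**The concern.** A sensitivity analysis of a missing-data rule should move what the rule sets aside. Here the primary rule sets aside three states and the four analyses move one of them, plus a fourth kind of unknown (missing special-interest contraindications) that the primary rule does not mention. Missing posology has a named place in the sample-size allowance but in none of the four analyses. The two pairs are also run separately, so inconclusive indications and missing contraindications are never set to the same extreme at once.

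The study exists to judge whether the risk minimisation measures work. A regulator reading the non-adherence proportion needs to know how far undocumented items could shift it, above all upwards. If the four results are the only evidence on that question, the possible shift may be understated.

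**Working it through.** **1. The plan's own figures.** The target is "aiming for a precision (defined as the confidence interval width) of up to 5 percent points of the exact two-sided 95 % confidence interval", for rates starting at 5 % and ending at 95 %, so the widest case is 50 %. The Clopper-Pearson width at 50 % is 5.000 points for n = 1574 and 5.001 for n = 1573, so 1574 is correct. 1574 / 0.90 = 1749 after rounding up. For the fallback, n = 1098 gives 5.999 points and 1098 / 0.90 = 1220. All stated sizes reproduce. The 10 % covers inconclusive indication and missing posology together; the protocol does not split it.

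**2. Which unknown is moved where.**

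| Unknown item | Primary rule | Analyses 1, 2 | Analyses 3, 4 |
|---|---|---|---|
| Inconclusive indication | set aside | moved | no |
| Blank indication | set aside | no | no |
| Missing posology | set aside | no | no |
| Missing critical illness, sepsis or renal impairment | not stated | no | moved |
| Missing other contraindication | not stated | no | no |

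**3. Illustration.** Each unresolved patient is taken to have one unknown item that decides status, so the groups do not overlap. K is the number with known status and X the non-adherent among them. A, B, D and C are patients whose status depends on an inconclusive indication, blank indication, missing posology or missing special-interest contraindication. Unresolved patients leave the denominator until recoded.

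Assumed shares of N = 1749: A 5 %, B 1 %, D 4 %, C 3 %, with 30 % non-adherent among known. Only the 10 % total for inconclusive indication and missing posology has any basis in the protocol. Counts: A = 87, B = 17, D = 70, C = 52, K = 1749 − 226 = 1523, X = 457.

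- Primary: X/K = 457/1523 = 30.0 %
- Analysis 1: (X+A)/(K+A) = 544/1610 = 33.8 %
- Analysis 2: X/(K+A) = 457/1610 = 28.4 %
- Analysis 3: (X+C)/(K+C) = 509/1575 = 32.3 %
- Analysis 4: X/(K+C) = 457/1575 = 29.0 %
- Span of these five: 28.4 % to 33.8 %, **5.4 points**

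Joint recoding:

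- A and C together: 457/1662 to 596/1662 = 27.5 % to 35.9 %, 8.4 points
- with B added: 457/1679 to 613/1679 = 27.2 % to 36.5 %, 9.3 points
- with D added (all unknowns): 457/1749 to 683/1749 = 26.1 % to 39.1 %, **12.9 points**

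The four analyses thus stop 39.05 − 33.79 = 5.3 points short at the top and 28.39 − 26.13 = 2.3 points short at the bottom. The whole confidence interval is planned to be at most 5 points wide.

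**4. How the result depends on the assumptions.**

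- Known non-adherence of 10 % or 50 %: 5.4 against 12.9 points again.
- Missing contraindication counted as adherent unless recoded (the protocol does not state the primary rule): analyses 1 to 4 span 457/1662 to 544/1662 = 27.5 % to 32.7 %.
- Unresolved patients kept in the denominator throughout: 457/1749 to 544/1749 = 26.1 % to 31.1 %, 5.0 points against 12.9.
- The 10 % split as 5 % inconclusive and 5 % missing posology, no other gaps: 5.2 against 10.0 points (rounded).
- All 10 % inconclusive indications, no other gaps: 472/1749 to 647/1749 = 27.0 % to 37.0 % both ways. Nothing is lost.

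**The case against.** **The protocol never calls the four results bounds.** This stands. Section 9.7.1 describes a descriptive, exploratory study, and varying one factor at a time is ordinary practice. A reader might infer that the protocol presents analyses 1 to 4 as worst and best cases and so misstates them. The text makes no such claim.

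**A joint run could come in the statistical analysis plan.** It could, and its absence alone would not be a point against the protocol. But the protocol numbers four analyses and fixes what each recodes, and that set does not match the primary rule it is meant to test.

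**Blank indications will probably be few.** This also stands. The form has an inconclusive option, doubtful cases go to the prescriber, and empty fields are queried. Counts of missing values will be tabulated. It does not answer the gap for posology, which the plan itself expects to be missing in some patients.

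**Missing special-interest contraindications may be rare.** Section 9.3 says that information not available when the infusion started cannot be judged as non-adherence, which supports a recorded no. Section 9.9 still expects some contraindications to remain unassessable. The 3 % above is an assumption with no source in the protocol.

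**The joint limit is nearly recoverable by adding increments.** For the items that are moved, yes: 33.79 + 32.32 − 30.01 = 36.1 %, against 35.9 % for A and C together. No planned result allows the same for missing posology or blank indications.

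**Pairing analysis 1 with 3 and 2 with 4 would not give outer limits.** Correct. Even with blank indications added, that pair reaches 36.5 %, against 39.1 % once missing posology is included. It should not be described as the outer limits.

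**Conclusion.** The point holds as a mismatch between the primary rule and the analyses meant to test it. Missing posology and blank indications are set aside by the rule and moved by no sensitivity analysis, and no analysis moves the unknowns together. The span of the four results is narrower than the data allow whenever more than one type of unknown decides patients' status, or any status depends on missing posology or a blank indication. If inconclusive indications are the only gap, the span is complete.

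The size is unknown. The 5.4 against about 13 points rests on assumed shares, non-overlapping groups, and each unknown item deciding its patient's status. A patient already non-adherent on another item is unaffected by the unknown one, so real shares of deciding unknowns may be smaller than raw missing rates.

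A reader might go further and conclude that the primary proportion is biased, or that true non-adherence exceeds what will be reported. Neither follows: the documents say nothing about which way the unknown items would fall. This is a recommended change to the analysis rules and leaves the planned sample size untouched.

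**What to change.** 1. In Section 9.7.1, widen analyses 1 and 2 so that they recode an indication that is inconclusive or missing.
2. Add one joint pair over all eligible patients. Every unknown item that decides a patient's status (inconclusive or missing indication, missing posology, missing contraindication) is set to non-adherent in the first run and to adherent in the second. Report both beside the primary proportion, with the number of patients recoded for each type of item.
3. State how a missing contraindication is treated in the primary analysis, so that the joint pair starts from a defined rule.

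The cost is a short wording change and two further table rows. No new data and no change to the sample size are needed. The one downside is a wider reported range.

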9.7.2 Validity of Outcome Measures

Assessing non-adherence of hospital physicians to the PI specifications in a non-interventional and retrospective DUS can reduce potential bias. However, this DUS has potential limitations (see [Section 9.9](#)).

The aim to include several HES-accredited hospitals of several European countries and the intended consecutive inclusion of patients should provide a meaningful record of HES 130-containing medicinal products used in routine clinical practice.

9.8 Quality Control

The generation of the study protocol is based on the “Guidance for the format and content of the protocol of non-interventional post-authorisation safety studies” (EMA 2012)⁵.

Moreover, Sponsor’s and/or CRO’s standard operation procedures (SOPs) are used for planning, conducting, reporting and archiving of the study. Quality measures are defined in these SOPs.

9.8.1 Procedures in the Participating Hospital

Each hospital designates one principal investigator (who will be supported by the appointed CRO). The principal investigator will be responsible for:

- Obtaining local Independent Ethics Committee (IEC) approval (if required by local requirements) for the conduct of the DUS in his/her HES-accredited hospital
- Obtaining a waiver for signed written patient data protection consent if required according to HES-accredited hospital/national policy

DUS to Investigate the Routine Use of Hydroxyethyl Starch-containing Infusion Solutions

FK Study Identifier: HE06-027-CNI

- Assigning site staff and ensuring that the assigned staff is properly trained (e.g. for the study protocol and eCRFs)
- Ascertainment of data accuracy, i.e. he/she is responsible for a complete and correct recording of data in the eCRFs in the respective HES-accredited hospital (he/she should apply the four-eyes principle) to assure high quality of data. Therefore, source data verification on data entered by a specialised investigator regarding indication and contraindication (in eCRF) should be performed by trained study staff member (e.g. study nurse). Application of four-eyes principle could be documented in the eCRF. In case of unresolvable discrepancies, i.e. no conclusion could be reached between both persons regarding indication and contraindication, the final decision will be taken by the local principal investigator at the respective site
- Ensuring that only qualified study staff members conduct the following:
 - A specialised investigator (e.g. anaesthesiologist, emergency care physician; see [Section 9.3](#)) has to assess the cases, enter data, and verify the data regarding indication and contraindications in the eCRF (this also applies if changes regarding indication/ contraindications occur)
 - Investigators or delegated trained study staff members are allowed to enter data on Basic Information, posology (dosage), HES 130 trade name, hospital ward, main medical procedure, crystalloid use
- Notification to the CRO, in advance of documentation and at any time after start of documentation, if the retrospective recording is not or no longer possible or feasible (e.g. due to changes in the resource situation in the participating HES-accredited hospital).

Depending on national and local requirements, the CRO will facilitate tasks for the principal investigator, e.g. by compiling documents for submission/notification to the IEC and obtaining positive opinion, if necessary. Furthermore, the CRO will provide training material and will raise queries to the investigator regarding missing or inconclusive data recorded in the eCRF.

Each participating HES-accredited hospital will receive an Investigator Site File from the CRO prior to the start of the DUS, containing at least the following documents:

- DUS study protocol
- Manual for eCRF
- Documents of IEC
- Training slides for investigators and delegated qualified study staff
- CRO's and Sponsor's contact details

In addition to the programmed edit, logic and manual checks of the EDC system (see [Section 9.8.2](#)), source data verification on data entered by a specialised investigator regarding indication and contraindication in the eCRF should be performed by applying the four-eyes principle as defined above.

9.8.2 Procedures at the Contract Research Organisation (CRO) to Ensure Reliable Data Quality

Edit and logic checks will be specified in a data validation plan and will be programmed into the EDC system to ensure high-quality data. Missing/implausible data will be highlighted to the investigators and/or qualified study staff member at the participating hospitals and will be prompted to be corrected/completed. All requests to complete missing data fields in the eCRF will be shown during data entry to the sites by the EDC system, so that sites can readily access individual patient data to complete data if necessary.

As a quality assurance measure it is intended to perform a pre-testing including a medical review prior to conduct of the study in which the eCRF will be assessed to identify potential issues such as misunderstanding provided that sufficient time is granted. This will also help to reduce potential amendments during documentation of the study. After the “go live” of the EDC system, data management activities will include data review for consistency.

Qualified English speaking personnel at the CRO will be available during all regular working hours (9 am – 5 pm) to answer any immediate technical or procedural questions by the investigators or qualified staff members from the centres.

All data will be prepared, pseudonymised and stored in data formats that are suitable for external auditing and inspection at any time the need should arise.

The CRO is responsible for e.g. performing eCRF training and providing all relevant documentation to the investigator at each centre as specified in [Section 9.8.1](#).

The CRO will assign a secure login for investigators and/or qualified study staff who will be responsible for documentation. The secure login allows the investigators and/or qualified study staff to enter the data into the eCRF. The CRO will track assigned and withdrawn secure logins to the eCRF.

